## **3 Study Overview**

### **3.1 Study Design**

This is a phase 3 multicenter, double-blind, randomized, placebo-controlled, parallel-group study designed to evaluate the efficacy and safety of CSL112 on reducing the risk of MACE in subjects with ACS (diagnosed with STEMI or NSTEMI) who are receiving evidence-based medical therapy.

Subjects will be screened and, if eligible, stratified at baseline by index MI type (STEMI vs NSTEMI), management of the index MI (PCI vs medically managed), and region (North America, Latin America, Western Europe, Central and Eastern Europe, or Asia Pacific). A balanced distribution of STEMI and NSTEMI is desired, and may require implementation of a limit on an index MI type during the conduct of the study. The study will enroll approximately 17,400 subjects with recent MI, up to a maximum of approximately 20,600 subjects, who will be randomized with equal allocation (1:1 ratio) to 1 of 2 treatment groups (CSL112 6 g or placebo).

The study is planned to be conducted at approximately 1000 sites. The estimated study duration is approximately 50 months.

**Apolipoprotein A-I**

---

The study will consist of a Screening Period, an Active Treatment Period, and a Follow-up Period ([Figure 1](#)).

**First medical contact (FMC)** is defined as the documented time point (ie, clock start) when the subject arrives at the 1st treating hospital emergency department (ie, door time) or cardiac catheterization laboratory for evaluation and treatment of the index MI event. Eligible subjects meeting all inclusion criteria and none of the exclusion criteria ([Section 4.1](#)), and who meet dosing eligibility criteria ([Section 4.2](#)) will receive once weekly IV infusions of investigational product (CSL112 or placebo) for 4 consecutive weeks, with each infusion approximately 7 days apart (- 2 / + 1; ie, dosing between 5 to 8 days window) during the 4-week Active Treatment Period. Each infusion of investigational product should be completed as close to the visit windows outlined in the [Schedule of Assessments](#) as possible. An infusion may be skipped (ie, ‘missed’) or delayed at the discretion of the investigator to evaluate and treat an adverse event (AE) before the next infusion. Therefore, the time window between each infusion may be extended as long as the last infusion of investigational product is given within 30 days of infusion 1, and the minimum window between infusions is at least 5 days.

For all randomized subjects, before administration of infusion 1 of investigational product, each subject must be deemed clinically stable, must meet the renal and hepatic eligibility criteria, and be dosed within 5 days of FMC. In addition:

- For subjects treated medically with or without thrombolytic agents, infusion 1 of investigational product must occur no earlier than 12 hours after FMC.
- For subjects undergoing angiography or PCI, with or without stent placement, infusion 1 of investigational product must occur no earlier than 12 hours after IV contrast administration.

Infusion 1 should occur before hospital discharge or on the day of discharge. If discharge occurs on a weekend, infusion 1 of investigational product can be administered on the next business day as long as timing is still within 5 days of FMC. All tests and procedures that are required to be performed to determine subject eligibility (ie, screening and randomization) must be performed with enough time to administer the investigational product within this timeframe. Screening and randomization may occur on the same day (Day 1) provided laboratory results are available for review by the investigator and all eligibility criteria have been met, including the requirements for alanine aminotransferase (ALT), total bilirubin, and serum creatinine.

[figure not shown]
**Apolipoprotein A-I**

Study assessments will be conducted at screening (Visit 1), before and after infusions (Days 1, 8, 15, and 22 [Visits 2, 3, 4, and 5, respectively]), at Day 29 / Visit 6 (end of Active Treatment Period), Day 60 / Visit 7, Day 90 / Visit 8, and every 90 days thereafter up to Day 365 (Figure 1). During the Follow-up Period, the Day 60 / Visit 7 and Day 270 / Visit 10 assessments may be conducted by telephone. All other visits during the Follow-up Period will be conducted as in-person visits at the clinical site. The study will conclude at least 365 days after the last subject is randomized. Study assessments will be conducted as shown in the **Schedule of Assessments**.

Interim analyses for futility and efficacy will be conducted at scheduled intervals, and safety reviews will be performed periodically by the IDMC. These formal interim analyses will be performed at times based on accrual of the adjudicated primary 90-day MACE. Three planned interim analyses will be performed after observation of approximately 30%, 50%, and 70% of the event target for the primary MACE endpoint; the first and second interim analyses will be for futility only while the third interim analysis will be for efficacy only ([Section 10.3.6](#)). As part of the IDMC charter, criteria will be specified for early termination of the study for futility and efficacy. Based on event accrual, if the expected timing of the IDMC review of the 70% interim analysis is less than 2 months prior to the anticipated completion of study enrollment, the 70% interim analysis for efficacy will not be conducted.

During the course of study conduct, the IDMC will assess safety with respect to hepatic and renal function when the first 20% of enrolled subjects have completed Visit 6 (Day 29). In addition, the IDMC will review renal function for those subjects dosed within 12 to < 48 hours after contrast administration (see [Section 10.3.6.2](#) for further details).

**Figure 1** **Study Schema**

EOS = End of Study; FMC = first medical contact.

### **3.2 Dose and Dosing Regimen**

CSL112 (6 g) or a matched volume of placebo will be administered as an IV infusion into a suitable vein (peripheral or central) once weekly for 4 consecutive weeks (4 infusions total) ([Section 6.2](#)). The placebo used in this study is a physical match to the investigational product, CSL112, ([Section 5.1.2](#)) after proper preparation. A 6 g dose of CSL112 was selected for this study based upon the safety and PK / PD data obtained in the AEGIS-I study in subjects with MI (Study CSLCT-HDL-12-77).

Dosing eligibility criteria are presented in [Section 4.2](#).

### **3.3 Scientific Rationale**

#### **3.3.1 Study Design Rationale**

Despite advances in therapeutic strategies for ACS, patients are at high risk for early recurrent events, particularly in the immediate weeks to months following the event. Consequently, effective and safe therapies that provide clinically relevant reductions in recurrent CV events beyond current secondary prevention are needed for patients with ACS. Subjects with a recent MI have been chosen as the study population to best study this unmet need in the immediate weeks to months following the event. In addition to the key inclusion criterion of evidence of multivessel coronary artery disease (see [Section 4.1.1](#), Inclusion Criterion 5), subjects are required to have the presence of high cardiovascular risk, either the presence of diabetes mellitus requiring pharmacotherapy or at least 2 of the following risk factors: age of 65 years or older, prior history of MI, or peripheral arterial disease. This enrichment strategy selects subjects at highest risk for subsequent CV events after an MI and provides adequate representation of subgroups of interest.

A double-blind design is being used to avoid potential bias during data collection and evaluation of clinical endpoints. A placebo-controlled design is being used because there is no approved active comparator for CSL112; therefore, CSL112 will be evaluated compared with placebo. All subjects randomized to treatment (CSL112 or placebo) in the study will receive background evidence-based medical therapy according to local standards of care and national practice guidelines (without a local standard, the current guideline from the American College of Cardiology / American Heart Association, European Society of Cardiology, etc. should be utilized), which will allow assessment of the incremental impact of CSL112 over currently approved treatments.

The definition of FMC has been selected to best represent the time the subject first presents for treatment for an acute ACS event and allows for targeted treatments to be provided. The goals of early treatment are immediate relief of ischemia, and prevention of complications arising from the MI and death. Thus, the time period of FMC is the start of the observation when acutely targeted therapies can be administered. This time period best allows for the identification of patients who have clinical instability and do not meet eligibility criteria. All patients who are deemed clinically stable during this period, have no suspicion of AKI after IV contrast agent administration (subjects who have undergone angiography) or after FMC for the index MI (subjects who have not undergone angiography), and meet all eligibility criteria should be considered for participation in the clinical trial. In contrast to acute ACS therapies, CSL112 is being developed for use in high-risk ACS patients to reduce the risk of CV death, MI, and stroke during the sub-acute period post MI when patients continue to be at increased risk for recurrent events.

Because of the related pathophysiology of individual CV events such as death, MI, and stroke after the acute phase of ACS, composite MACE endpoints consisting of relevant and related components have become accepted as primary endpoints in the study of new agents in ACS studies [[CPMP/EWP/570/98, 2016](#)]. Cardiovascular death, MI, and stroke are the most clinically meaningful efficacy endpoints for CV clinical studies as they are distinct irreversible events. The treatment focus for CSL112 is the subacute (ie, short term) period when patients recovering from ACS are most vulnerable for recurrent events. Therefore, to assess clinical benefit of CSL112, the primary endpoint of MACE at Day 90 is an appropriate timepoint. The durability of CSL112 will be assessed using the key secondary endpoints of MACE at Day 180 and extended follow-up at Day 365.

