## **10           Statistics**

### **10.1 Sample Size**

#### **10.1.1       Estimation**

The study is designed as a superiority study. The sample size calculation is based upon the hypothesis that compared with placebo, CSL112 will have a 20% relative risk reduction (hazard ratio = 0.80) in the primary endpoint over 90 days of follow-up after randomization (ie, all subjects will be followed for a fixed duration of 90 days after randomization).

Assuming a 1-sided alpha of 0.025, not accounting for any dropouts from the study, and the interim analyses specified below, 1004 confirmed MACE (CV death, MI, or stroke) will provide at least 90% power. A 1-sided hypothesis test is necessary to differentiate directionality for interim analyses of futility and efficacy. Based on an assumed 90-day placebo event rate of 6.4%, an estimated 17,400 subjects (8700 per group) will be required.

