**Apolipoprotein A-I**

---

The target number of events is also sufficient to achieve a 1-sided  $P$  value of 0.005 (approximate) with an observed hazard ratio of 0.85 in the primary endpoint and will afford at least 69% power to detect the minimally clinically relevant hazard ratio of 0.85.

The sample size calculation given above for number of required events and number of estimated subjects includes 3 formal interim analyses. The first 2 interim analyses will be conducted for futility only after observation of approximately 301 confirmed MACE (30% of the total target number of events) and 502 confirmed MACE (50% of the total target number of events). The third interim analysis will be conducted for efficacy only after observation of approximately 703 confirmed MACE (70% of the total target number of events).

The definition of futility boundary value is based on a 2-sided 95% confidence interval for the interim hazard ratio and a conclusion of no true underlying treatment difference will be reached if the confidence interval excludes a hazard ratio of 0.8 which is the hypothesized treatment effect. Specifically, the stopping boundary (non-binding) for futility will be crossed at the first interim analysis if the observed hazard ratio is  $\geq 1.003$  (1-sided  $P$  value  $\geq 0.51$ ), assuming the analysis is performed with 301 events. At the second interim analysis for futility, the stopping boundary on the hazard ratio scale is defined to be 0.953 (1-sided  $P$  value  $\geq 0.295$ ) assuming the number of events is exactly 50% of the target (502 events). The cumulative probabilities of meeting the futility thresholds at the first or second interim analyses if there is no true underlying treatment difference (ie, a true hazard ratio of 1) are 0.49 and 0.735, respectively.

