#### **10.3.2.2.1      Primary Efficacy Analysis**

The primary analysis of time to the 3-component MACE (CV death, MI, or stroke) will be based on a covariate-adjusted Cox regression model including fixed effects for treatment, region, index MI type, index MI management, age (as a continuous variable), diabetes, peripheral artery disease, history of prior MI (excluding index MI) and a term for interaction between index MI type and index MI management will be fitted using the PHREG procedure in SAS. The 1-sided Wald  $P$  value for hypothesis testing, the hazard ratio and its 2-sided 95% confidence interval, will be estimated from the model. The primary statistical analysis will utilize the ITT Analysis Set. Statistical significance will be assessed using a 1-sided 0.000083 alpha level at the efficacy interim look and 0.024999 at the final analysis (if the primary null

hypothesis is not rejected at the 70% interim analysis) assuming the number of events accrued is exactly the same as the target, ie, 703 and 1004 at the interim and final analyses, respectively. The actual significance level will be recomputed using an alpha spending function at the time of analysis if the observed number of events is different from that expected. Cumulative event rates will be calculated using the KM method. The effect over time will be illustrated with a plot of the complement (1 – KM) of KM estimates. Event counts and percentages will be summarized. Analysis under the ITT Analysis Set will utilize the strata to which subjects were randomized regardless of any errors in the randomization process.

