4.5 Determination of Sample Size

The sample size calculation was performed using East 6.4 and is based upon the hypothesis that compared to placebo, CSL112 will achieve a 20% relative risk reduction (hazard ratio of 0.80) in the primary endpoint over 90 days of follow up from the time of randomization. With this design, the total number of events required is 1004 and the total estimated sample size is 17,400 subjects.

The following assumptions were made in calculating the sample size:

- A 90-day MACE event rate of 6.4% in the placebo arm based on Duke Clinical Research Institute ACS Clinical Trial Database
- A hazard ratio (CSL112: Placebo) of 0.8 under the alternative hypothesis and 1.0 under the null hypothesis
- A 1:1 allocation scheme

- Approximately 91.9% chance of successfully claiming superiority in the presence of a true underlying difference
- A 2.5% chance of erroneously claiming superiority in the presence of no true underlying difference, ie, 1-sided 2.5% significance level
- Recruitment time of 38 months
- A fixed duration of follow-up equal to 90 days for primary efficacy assessment
- 3 interim analyses (at 30%, 50%, and 70% of expected confirmed event target) and 1 final analysis; first and second interim analyses will be for futility only while the third interim analysis will be for efficacy only
- Futility bounds determined on the hazard ratio scale such that the lower limit of a two-sided 95% confidence interval (CI) for the hazard ratio excludes the hypothesized treatment effect; ie, a hazard ratio of 0.8
- A stopping boundary from the Rho [Kim and DeMets, 1987] family alpha-spending function with a parameter value of 16 to evaluate whether to stop early for dramatic benefit at the expected confirmed event target of 70%
- Hypothesis testing with a 1-sided log-rank test

Under these assumptions, a total of approximately 1004 adjudicated, CEC confirmed MACE events with an estimated total sample size of 17,400 subjects will afford the trial greater than 90% power to reject the null hypothesis. The target estimated number of events is also sufficient to achieve a 1-sided P value of 0.005 (approximate) with an observed hazard ratio of 0.85 in the primary endpoint; ie, time to first occurrence of any component of MACE (CV death, MI, or stroke). In addition, if the assumed hazard ratio is 0.85 (the minimally clinically relevant hazard ratio), 1004 events would provide at least 69% power.

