In addition, for descriptive purposes, hospitalizations per thousand subject-years of follow-up will be summarized by treatment group.

The leading analysis of the hospitalizations endpoint described above is focused on the estimation of a rate ratio (CSL112: placebo) to determine whether treatment with CSL112 reduces the mean number of hospitalizations during the 90 day period. This approach accounts for death indirectly by adjusting the mean incidence for the duration of exposure but otherwise ignores death in the analysis. Thus, it provides a pharmacoeconomic assessment of treatment benefit afforded by CSL112.

A sensitivity analysis of the hospitalization data will be performed to explicitly incorporate death into the outcome using the Win Ratio [[Pocock et al, 2012](#)] method. This approach recognizes clinical hierarchies within composite outcomes. With the planned endpoint, death will be weighted more heavily relative to the total number of CV hospitalizations during 90 days from the time of randomization. The Win Ratio (CSL112: Placebo) will be calculated along with associated 95% CI and a 1-sided P value. A complete description of the analytical approach is given in [Appendix 15.1](#).

10.2.2 Time to first occurrence of CV Death, MI, or stroke from the time of randomization through 180 days

The derivation of time to first occurrence of CV Death, MI, or stroke from the time of randomization through 180 days is given below. The analytical details are similar to that described for the primary efficacy endpoint and hence a general description is given here.

	Time to Event (days) [TTE]	Censoring Status [Censor]
First of positively adjudicated CV Death, MI, or stroke during the 180 days following randomization	(date of MACE – randomization date) + 1	0
Last MACE ascertainment on or after 180 days of follow-up without experiencing MACE of interest (administrative censoring)	180	1
Discontinue prior to 180 days without experiencing MACE	(date of last MACE assessment – randomization date) + 1	1
Experience non-CV death prior to day 180	(date of death – randomization date)+1	1

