Cumulative event rate through 180 days will be calculated using the Kaplan-Meier method. The summary will include the number of subjects with events, number administratively censored as well as number of non-administratively censored subjects. The effect over time will be illustrated with plot of the complement (1 - KM) of Kaplan-Meier estimates. Event counts and incidence rates will be summarized including point estimates and 95% CI s by treatment group.

A covariate-adjusted Cox proportional hazards regression model including fixed effect for treatment, region, index MI type, index MI management, age (as a continuous variable), diabetes, peripheral artery disease, history of prior MI (excluding index MI), and a term for interaction between index MI type and index MI management will be fitted to the data based on the PHREG procedure in SAS. The results from the Cox model will be summarized in a table including number (%) of subjects with events, estimated hazard ratio for treatment, its 95% CI and a 1-sided Wald *P* value for treatment comparison.

A supportive listing of individual subject data including the time to event in days and the censoring variable will be presented.

10.2.3 Time to first occurrence of CV Death, MI, or stroke from the time of randomization through 365 days

The analytical approach as outlined in Section 10.2.2 will also be applied to time to first occurrence of CV death, MI, or stroke from the time of randomization through 365 days.

A tipping point analysis will be performed to assess the impact of missing follow-up time in subjects who complete the study earlier than study day 365. Missing event times in the placebo arm will be imputed from subjects completing 365 days of follow-up under a CAR assumption while missing event times in the CSL112 arm will be imputed under increasing hazards of MACE (δ) to ascertain whether the conclusion from the leading analysis of the endpoint can be nullified. The clinical plausibility of the delta value at the tipping point, if reached, will be assessed. Hazard ratios and 95% CIs corresponding to each value of delta will be summarized.

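### The 180- and 365-day MACE tests offered as the assessment of durability re-count the first 90 days, so they can show that an early gain is kept but not that CSL112 has any effect after Day 90

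*Protocol*

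**What the plan says.** The design rationale (Protocol 3.3.1) gives the two later MACE endpoints a specific job: "The durability of CSL112 will be assessed using the key secondary endpoints of MACE at Day 180 and extended follow-up at Day 365". It does not define durability.

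Both endpoints start at randomization (Protocol 2.2.2 and 10.3.2.3.1). The SAP's 180-day derivation counts the "First of positively adjudicated CV Death, MI, or stroke during the 180 days following randomization" (SAP 10.2.2). For 365 days, SAP 10.2.3 says: "The analytical approach as outlined in Section 10.2.2 will also be applied to time to first occurrence of CV death, MI, or stroke". Each is analysed with the primary analysis's covariate-adjusted Cox model, with a single treatment term over the whole period.

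Testing is sequential (Protocol 10.3.2.5, SAP 7.4). The 180-day hypothesis (H03) is tested, with the hospitalization hypothesis (H02), only after the primary (H01) is rejected. The 365-day hypothesis (H04) is tested only if both H02 and H03 are rejected.

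Other planned items come close to the question:
- Event rates by arm at 90, 180 and 365 days, and 1-KM plots.
- A log-cumulative-hazard check of proportional hazards, followed if needed by an unspecified sensitivity analysis. It is written for the primary endpoint (SAP 10.1) and reaches the later endpoints only because their details are called similar.
- A 365-day tipping-point analysis, which addresses missing follow-up.

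Only procedures for cerebral or peripheral ischemia are split into Day 91-180 and Day 181-365 (SAP 9.5). No MACE analysis is.

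**The concern.** Treatment is four weekly infusions, so it is a real question whether any effect on MACE continues after Day 90. An average hazard ratio fitted from Day 0 mixes the early and late periods. It is also formally tested only when a significant early result is already inside it. A significant result at Day 180 or Day 365 is therefore expected both when the effect persists and when the drug does nothing further after Day 90. A report that follows the rationale's wording could present such a result as a lasting treatment effect, and no planned estimate would let the reader check.

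**Working it through.** **Reproducing the plan's power.** The design assumes that "CSL112 will have a 20% relative risk reduction (hazard ratio = 0.80) in the primary endpoint over 90 days of follow-up after randomization" and that "1004 confirmed MACE (CV death, MI, or stroke) will provide at least 90% power" (Protocol 10.1.1). For a fixed design, z = |ln 0.80| × √1004 / 2 = 3.54, and Φ(3.54 − 1.96) = 94.2%. Simulating the score process with the stated futility bounds (hazard ratio 1.003 at 301 events, 0.953 at 502) and the efficacy look at 703 events gives 92.0%. SAP 4.5 states "Approximately 91.9% chance of successfully claiming superiority in the presence of a true underlying difference". At a hazard ratio of 0.85 the simulation gives 69.5%; Protocol 10.1.1 says the events "will afford at least 69% power to detect the minimally clinically relevant hazard ratio of 0.85". The inputs are read correctly.

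**Inputs from the documents.** 8700 subjects per arm, 6.4% placebo rate at 90 days, hazard ratio 0.80 to Day 90, no dropout.

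**Assumptions.** The hazard ratio is exactly 1.00 after Day 90. The share s of 365-day placebo first events that fall by Day 90 is 50% to 80%. The documents give no 365-day rate. Protocol 1.1 reports that, in a cited ACS trial, about half of one-year events fell in the first 30 days, which makes 50% by Day 90 a cautious lower end.

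**Formulas.**
- Placebo cumulative hazard at Day 90: −ln(1 − 0.064) = 0.0661. CSL112 risk at Day 90: 1 − exp(−0.8 × 0.0661) = 5.15%.
- Early events: 8700 × (0.0640 + 0.0515) = 1005. Risk difference at Day 90: 6.40 − 5.15 = 1.25 points.
- Placebo risk at Day 365: 6.4% / s. Late hazard: −ln(1 − 0.064/s) − 0.0661, the same in both arms.
- Average ln HR = ln 0.80 × 1005 / (all events). z = |ln HR| × √(all events) / 2. Power = Φ(z − 1.96).

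| s | Placebo / CSL112 risk at Day 365 | Events, total (late) | Average HR | Nominal power | Given a primary win | Risk difference at Day 365 |
|---|---|---|---|---|---|---|
| 50% | 12.80% / 11.64% | 2126 (1121) | 0.90 | 68% | 72% | 1.16 points |
| 65% | 9.85% / 8.65% | 1609 (604) | 0.87 | 80% | 84% | 1.20 points |
| 80% | 8.00% / 6.77% | 1285 (280) | 0.84 | 88% | 92% | 1.23 points |

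The column given a primary win treats the early and late z-scores as independent and keeps only runs with early z > 1.96.

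**Day 180.** With 0.2 to 0.5 late events (Day 91-180) per early event, also an assumption, the nominal test succeeds in 87% to 95% of trials that win the primary, with interim looks included.

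**Contrast.** In patient-level simulations of the HR 0.80 and HR 0.85 scenarios with no late effect, a test restricted to Day 91 onward was significant about 2% to 3% of the time, close to its nominal 2.5%.

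**Sensitivity to the early effect.** With 0.5 to 1.0 late events per early event, Day 365 success given a primary win is 75% to 87% at an early hazard ratio of 0.80, 58% to 73% at 0.85, and 49% to 65% at 0.884.

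**The case against.** The strongest reply is that, for a short course aimed at the subacute period, durability may simply mean that the early gain is still there later. A cumulative, fully randomized comparison is the right tool for that, and this stands. In the scenario above the absolute difference goes from 1.25 points at Day 90 to between 1.16 and 1.23 at Day 365, so 93% to 98% is kept. A significant result there is a correct statement about cumulative benefit. The test also responds to loss: with a late hazard ratio of 1.10 it succeeds in 22% of trials where 43% of the absolute gain survives (s = 50%) and in 78% where 85% survives (s = 80%).

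A reader might infer that the plan would declare durability from a significant H03 or H04. The documents do not support that. The sentence in Protocol 3.3.1 is design rationale, no success rule links either test to a durability claim, and both hypotheses are already worded as running from randomization. A reader might also want the post-Day-90 hazard ratio to decide the matter. That goes too far, because the comparison is among subjects still event-free at Day 90 and is no longer fully randomized.

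The planned event rates and 1-KM plots would show curves that converge or stay parallel. They give no post-Day-90 estimate and no interval for the risk difference, so they reduce the gap without closing it.

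The percentages are for the nominal test. H04 also needs H02 rejected, and no effect size is given for H02. If H02 fails, H03 is in effect tested at 0.0125, which lowers Day 180 success given a primary win to about 79% to 88% (0.25 to 0.5 late events per early event).

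**Conclusion.** The point holds as a limit on what H03 and H04 can show. They measure cumulative benefit. They cannot separate a continuing effect from the Day 90 result carried forward, and nothing else planned for MACE does so with an estimate. With no effect after Day 90, the nominal Day 365 test still succeeds in about 68% to 88% of trials, or 72% to 92% given a primary win. This rests on the design effect of 0.80 being real to Day 90 and on the assumed 50% to 80% early share; a weaker early effect lowers it. The type I error of both tests as hypotheses about cumulative MACE is not in question. This is a cheap improvement, not a defect in the confirmatory analysis.

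**What to change.** In SAP 10.2.2 and 10.2.3, add as supportive analyses outside the gatekeeping:
- A treatment-by-period term, split at Day 90, in the same Cox model. Report hazard ratios with 95% CI for Day 0-90 and Day 91-180 (10.2.2) and for Day 0-90 and Day 91-365 (10.2.3).
- Kaplan-Meier risk differences with 95% CI at Days 90, 180 and 365.
- A statement that H03 and H04 measure cumulative benefit, and that significance alone is not evidence of an effect after Day 90.

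Alpha and testing order do not change, and no new data are needed. The cost is SAP wording, one model term and a few table rows.

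The downside should be written next to the analysis. The post-Day-90 hazard ratio conditions on being event-free at Day 90, and it is imprecise. With about 280 to 1120 late events by Day 365, its 95% CI runs from the estimate divided by to multiplied by exp(1.96 × 2/√280) = 1.26 at the low end, or exp(1.96 × 2/√1120) = 1.12 at the high end. With about 300 late events, power to detect a persisting hazard ratio of 0.80 is only 49%. It should inform interpretation alongside the risk differences and not be the sole criterion for durability.
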